6.7 Number of Investigational Sites

This feasibility study will be conducted at up to four investigational sites. The University of Maryland Medical Center (UMMC), would continue to be the lead center.

6.8 Methods to Reduce Bias and Conduct of the Investigation

This is an exploratory study that will be conducted in compliance with GCP guidelines, with analysis that is objectively based on temperature measurements with pre-specified success criteria, so bias is not expected to be a significant concern.

6.9 Intracranial Pressure Monitoring

No material response increase in intracranial pressure (ICP) is expected due to the use of COOLSTAT therapy. As noted herein, the first 5 study subjects will be required to have ICP monitoring in place in order to allay any related concerns. Additionally, ICP data will be collected manually for all subsequent subjects that already have intracranial pressure monitoring in place. The PI will report to the DSMB and Sponsor if a material change (increase) in ICP is attributed to the use of the COOLSTAT. The DSMB will be reviewing the initial five (5) cases to assess the impact on ICP of using the COOLSTAT.

6.10 Transition from 8-hour Cooling to 24-hour Cooling

The first 10 subjects will only be cooled for an 8-hour period, the results of which will be reviewed by the DSMB. For these first 10 subjects, if the subject still requires cooling at the end of 8 hours, the clinical site normothermia standard of care protocol will be used. If approved by the DSMB, the remaining subjects will transition to 24-hour cooling only upon satisfying all of the following criteria:

- No significant adverse events (SAEs) attributed to CoolStat
- CoolStat satisfied primary efficacy endpoint and success criteria on first 10 subjects (as specified herein):
 - 8 out of 10 subjects were cooled to $\leq 37.5^{\circ}\text{C}$ within 4 hours (based on final study endpoint of 75% subject achievement of this criteria)
 - 8 out of 10 subjects had core temp maintained between 37.5°C and 36°C for 80% of the steady state time following the initial achievement of 37.5°C .
- No findings of concern from ENT visual exam of upper airway post cooling
- Tympanic $> 34^{\circ}\text{C}$ and $< 39^{\circ}\text{C}$ during 8 hours of cooling, with no sustained period of more than 5 minutes $< 34^{\circ}\text{C}$ or more than 4 hours $> 39^{\circ}\text{C}$.
- No sustained increase of systolic blood pressure for > 5 minutes despite standard of care interventions that were above UMMC standard limits (specific to the indication being treated).
- DSMB reviews CRFs and agrees to increasing test period to 24 hours

6.11 Potential Inclusion of Subjects with a Past History of Cardiac Arrhythmia

- Subjects with a history of cardiac arrhythmia will continue to be excluded from the study for subjects #11-20, who will receive up to 24 hours of cooling.
- In the absence of any reports of occurrence of arrhythmia in this set of 10 subjects, then history of cardiac arrhythmia may be removed from the exclusion criteria for the subsequent subjects after review and approval by the DSMB.
- In the event that cardiac arrhythmia does occur during cooling in any of the remaining subjects, history of cardiac arrhythmia will be reinstated to the exclusion criteria.

7.0 Subject Recruitment and Enrollment

7.1 Patient Recruitment

Patients will be recruited for participation in this study from the population of patients in the Neurosciences Critical Care Unit (NCCU) who have an ischemic or hemorrhagic stroke, seizure, or metabolic encephalopathy, are intubated, and their expected stay in the NCCU is > 24 hours. We will only enroll patients with these diagnoses for whom the attending intensivist would otherwise prescribe an active cooling device to treat the patient's fever. The investigator or their designee will review the patient's medical history for eligibility based on the study's inclusion/ exclusion criteria. If the patient is determined to be eligible, either the patient or their legally appointed representative (LAR) will be approached by the PI or their designee to discuss the study and the patient's potential enrollment. Background on the study as well as risks will be provided as part of the informed consent form for review. If the patient or their LAR agree to participate, they will then sign the informed consent form, knowing that the patient can withdraw from the study at any time.

7.2 Point of Enrollment and Therapy Initiation Defined

A subject is considered **enrolled** in the study once the following have occurred:

- informed consent has been given by the subject or their LAR, and
- it is determined that the subject meets all of the inclusion criteria and none of the exclusion criteria.

A subject may be approved for COOLSTAT Therapy once the following additional screening criteria have been met after enrollment:

- the subject has developed a fever (core temperature $\geq 38.3^{\circ}\text{C}$) and has remained febrile for at least one hour after the administration of antipyretics (institutional

standards will be followed with respect to duration of antipyretic administration before initiation COOLSTAT Therapy),

- it is confirmed that the subject has a core temperature probe (either esophageal, SpotOn or bladder), and
- an ENT exam is performed (if not done previously to enrollment) to evaluate for craniofacial abnormalities that would exclude the subject.

If the subject does not meet these criteria within 7 days from enrollment, the subject will be withdrawn from the study as a post-consent screening failure and is not eligible for intervention. No further follow-up will be required.

Due to the unpredictable nature of fever development and persistence, the study will be overenrolled in anticipation of many patients not proceeding to fever refractory to antipyretic treatment. The Table of Events below demonstrates the sequence of study activities related to enrolling patients, and then monitoring for eligibility for COOLSTAT therapy.

Table of Study Events

	Admitted to NCCU	Enrolled- Observe for Fever up to 7 day	Many enrolled patients will ultimately not be eligible as fever is unpredictable	Develops Fever Refractory to Antipyretics Treatment	Phase 0	Phase I	Phase II	Phase III
Evaluate for Inclusion/ Exclusion Criteria	X	X			X			
Obtain Informed Consent	X							
ENT Exam		X		X (if not during observation)				X
Antipyretic Treatment Upon Development of Fever	X	X		X	X	X	X	X

Initiate COOLSTAT Treatment				X		
Continuous Monitoring (ICU SOP) ¹	X	X	X	X	X	X
Study Phase Description			30 min. pre-therapy monitoring	8 or 24 hrs. of therapy	2 hrs. post-therapy monitoring	22 hrs. post-therapy monitoring

¹Subject monitoring includes core and tympanic temperatures, blood pressure, intracranial pressure (when available), suctioned water volume, and level of shivering.

8.0 Study Inclusion and Exclusion Criteria

8.1 Inclusion Criteria

Male or female subjects may be included in the study if he/she meets ALL of the following inclusion criteria:

1. Admitted to the Neurosciences Critical Care Unit (NCCU).
2. Patient has ischemic or hemorrhagic stroke, seizure, or metabolic encephalopathy.
3. Patient is orally intubated or has tracheostomy tube and is mechanically ventilated.
4. Planned stay in NCCU > 24 hours.
5. Must have informed consent from the patient or the legally authorized representative (LAR) making decisions for the patient.

8.2 Exclusion Criteria

A male or female subject will be excluded from the study if he/she meets ANY of the following exclusion criteria:

1. Age < 18 years old or > 95 years.
2. Intubation is contraindicated.
3. With a coagulopathy. INR above 1.5 or PTT above 45 seconds.
4. Hemodynamic instability, including elevated SBP for >5 minutes despite standard of care interventions (SBP \geq 160 mmHg for intracerebral hemorrhagic stroke; SBP \geq 220 mmHg for subarachnoid hemorrhagic stroke or ischemic stroke).
5. History of cryoglobulinemia.

6. History of sickle cell disease.
7. History of serum cold agglutinin disease.
8. Active/ongoing nose bleeds.
9. Known or suspected pregnancy.
10. Participation in another ongoing investigational study.
11. Prisoners and/or patients for whom no LAR is available.
12. Patient is in airborne/droplet disease isolation protocol.
13. Patient is or suspected to be immunocompromised;
14. Low platelet count defined as < 100k (thrombocytopenia).
15. Nasal septal deviations (per CT scan; any degree).
16. Chronic rhinosinusitis.
17. Prior skull-based surgery.
18. Penetrating cranial trauma.
19. Recent nasal trauma or anterior base skull fracture.
20. Presence of cardiac arrhythmias including: sustained tachycardia defined as heart rate above 120 beats per minute, or sustained bradycardia defined as heart rate below 60 beats per minute.
21. Refractory hypoxemia defined as partial pressure of oxygen in arterial blood (paO₂) below 60 torr or oxyhemoglobin saturation below 90% despite endotracheal intubation, mechanical ventilation, and provision of supplemental oxygen of up to 0.60.
22. Refractory hypercarbia defined as partial pressure of carbon dioxide in arterial blood (paCO₂) above 50 torr despite endotracheal intubation and conventional mechanical ventilation.
23. History of cardiac arrhythmia as listed above.
24. BMI of $\leq 15 \text{ kg/m}^2$ or $\geq 40\text{kg/m}^2$

9.0 Sequence of Investigational Assessments and Procedures

9.1 Study Team Member Activities to Assess Eligibility for Cooling

Potential candidates for the study are evaluated by the Investigator or their designee.

1. The investigator or their designee must approve the candidate to be enrolled by confirmation of inclusion / exclusion criteria, including the informed consent received from the patient or the patient's Legally Appointed Representative (LAR).
2. Every 12 hours, from time of enrollment up to 7 days, the volume of fluid collected from tracheal suction will be recorded. (The volume of oral fluid suctioned from the subject should not be collected with other suctioned fluids.) These volumes will be averaged to be used as a baseline for comparison to fluid volumes collected during the use of the CoolStat device.
3. The investigator may approve the enrollee for COOLSTAT therapy if all of the following are satisfied within 7 days of enrollment:
 - the subject has or develops a fever (core temperature $\geq 38.3^{\circ}\text{C}$, but $<39.5^{\circ}\text{C}$) and remains febrile for at least 1 or 2 hours (based on institutional standard) after the administration of antipyretics,
 - the subject is confirmed to have core temperature probe (esophageal, SpotOn or bladder), and
 - an ENT exam is performed (if not done previously to enrollment) to evaluate for craniofacial abnormalities that would exclude the subject.
4. The investigator shall withdraw the subject if the above criteria are not met within 7 days after "enrollment". No further monitoring or follow-up is required for such subjects.

9.2 Phase 0 – Monitoring Before Cooling

1. Prior to starting the COOLSTAT device, clinical personnel will confirm that the subject is intubated and mechanically ventilated.
2. The COOLSTAT device shall be brought into the subject's room and the core temperature sensor (either esophageal - Smiths Medical Esophageal Stethoscope Temperature Sensor; Series 400. Model ES 400-12 - or bladder - Foley Catheters, BARDEX® I.C., Temperature-Sensing, Dual Connector 5 mL balloon, 16 French - or 3M Spot On™ Temperature Monitoring System) will be plugged into the COOLSTAT device. The subject's core temperature should be confirmed at this time to be $\geq 38.3^{\circ}\text{C}$, but $<39.5^{\circ}\text{C}$, as displayed on the CoolStat device.
3. Delivery of any medications or other fluids orally will be recorded on the CRF due to potential temporary effect on esophageal temperature probe. Even room temperature fluids may affect the temperature reading, and time of administration should be recorded.
4. A tympanic temperature sensor will be placed in the subject's ear and connected to the hospital's temperature monitoring system to record temperature. The acceptable tympanic temperature range is 34 to 39°C, and the hospital system temperature alarms will be set to indicate any readings outside that range. NOTE – in this study, tympanic

temperature is only considered as a surrogate for brain temperature for safety monitoring. Either esophageal or bladder temperature will be used as core temperature. It can take about 5 to 10 minutes for the tympanic temperature sensor to reach a steady state monitoring condition when initially placed in the subject's ear.

- 5. The COOLSTAT device will be prepared and the set up initiated, but not turned on. COOLSTAT set up and operation procedures are provided in the Operator's Manual, as well as a Quick Start Guide.
- 6. The subject target temperature will be set to 36.5 °C on the CoolStat device.
- 7. The subject's core temperature will be monitored and recorded in the CRFs, from the esophageal, SpotOn, or bladder temperature sensor. The acceptable core temperature range is 36°C to 39°C. The patient may remain >39.0 °C but <39.5 °C for up to 4 hours, at which point the CoolStat treatment will be discontinued and an alternative cooling method initiated. Likewise, the CoolStat will be stopped if the subject has a sustained core temp > 39.5 C sustained for 5 minutes.
- 8. Position of the endotracheal tube will be verified and recorded in CRF (distance measured at subject's teeth), per normal procedure.
- 9. For the first 5 subjects, ICP monitoring and measurement of < 20 mmHg will be confirmed.
- 10. The subject will be monitored, without turning on the COOLSTAT, for 30 minutes to ensure the subject's temperature is stable and febrile. Over this time period, an assessment will also be made to assess blood pressure and ICP (if available) of the subject, which will be recorded in the CRFs.
- 11. A bolus dose of meperidine (Demerol) may be given to the subject prior to starting the COOLSTAT device to dampen a potential pain response to the COOLSTAT therapy. This can be given 15 minutes into Phase 0 recording (and therefore 15 minutes prior to initiation of COOLSTAT therapy; see explanation below).
- 12. Upon starting the cooling therapy, the provided stopwatch is started and the start time is recorded on the therapy monitoring form. The time will also be recorded from a room clock (with source noted) to facilitate alignment of data records.

Each investigational site will follow their standard procedures for managing shivering and active cooling tolerability in their patients.

9.3 Phase 1 – Active Cooling Phase

Subjects will receive COOLSTAT cooling treatment, with a maximum of 30 cmH₂O of air pressure (as automatically controlled by the device). The COOLSTAT will be operated in closed-loop control mode and will automatically modulate and control air flow and maintain the subject's core temperature between 36 °C and 37.5 °C, as measured by the esophageal, SpotOn, or bladder temperature sensor. The device will be set to target 36.5 °C.

The COOLSTAT will attempt to cool to and maintain this temperature range over the phase period. The core temperature will be recorded automatically by the COOLSTAT device, and is displayed on the COOLSTAT screen.

While the COOLSTAT is in use, no other cooling therapies will be used other than antipyretics.

Throughout Phase 1, the subject's temperature and vital signs will be monitored per NCCU protocol, as well as data collected in the CRFs. If any alarms occur, the appropriate action will be taken as described herein. COOLSTAT device errors will be addressed via an available trained technician and study team training (See Operator's Manual for a description of the possible device errors). Treatment may be discontinued at any time if adverse events are encountered or alternate cooling methods are required on an urgent basis. The Investigator or their designee must review any such emergency changes to therapy and complete an Adverse Event form detailing the reason for the change.

Per standard of care in the NCCU, maximum allowed limits will be imposed for a sustained increase in SBP >5 minutes above existing SBP threshold limits (specific to the indication being treated) despite standard of care intervention. In this event, COOLSTAT use will be discontinued for that subject. Once the COOLSTAT is discontinued due to SBP elevation, it will not be restarted for that subject. However, the study team will continue to monitor SBP to see if it recovers back to baseline value after the COOLSTAT is turned off. The Investigator or their designee must complete an Adverse Event form detailing the event and the value of the SBP prior to, during and after the COOLSTAT was used.

Similarly, per standard of care in the NCCU, a maximum allowed limit will be imposed for a sustained increase in ICP >5 minutes above max threshold despite standard of care intervention (using existing max institutional limits for the indication being treated). In this event, COOLSTAT use will be discontinued for that subject. Once the COOLSTAT is discontinued due to ICP elevation, it will not be restarted for that subject. However, the study team will continue to monitor ICP to see if it recovers back to baseline value after the COOLSTAT is turned off. The Investigator or their designee must complete an Adverse Event form detailing the event and the value of the ICP prior to, during and after the COOLSTAT was used. See Section 10.0 on procedures following the occurrence of an Adverse Event.

The Investigator or their designee will perform an initial cooling assessment 4 hours after COOLSTAT cooling has begun to determine if the subject has reached normothermia (≤ 37.5 C) sometime within the 4-hour cooling period. Starting from the initiation of normothermia, a subject's core temperature may fluctuate (within about 36.0-37.5 C), but

Transnasal Induction of Normotherapy in NCCU Fever Patients

if the core temperature $>39.0^{\circ}\text{C}$ for 4 hours, CoolStat treatment will be stopped and the subject will be switched to an alternative cooling method. If normothermia ($\leq 37.5^{\circ}\text{C}$) is not achieved within the 4-hour period, the Investigator or their designee will remove the subject from the COOLSTAT device. The subject will be classified as a treatment failure and placed on standard of care treatment at the discretion of the Investigator or their designee and manual data collection will continue per the instructions for Phase 2 in Section 9.4. NOTE – if the Investigator feels that the subject's temperature is approaching the target and the subject is being adequately cooled, CoolStat device operation can be allowed to continue beyond the 4-hour period. The Investigator should note if this is the case in the CRF.

If a subject must be disconnected from the CoolStat device for transport from the NCCU to another unit (e.g., to radiology or angiography suite), they will be reconnected to the device at steady state if their core temperature upon being reconnected to the CoolStat is $\leq 37.5^{\circ}\text{C}$. If the subject's temperature is $> 37.5^{\circ}\text{C}$ upon being reconnected to the device, the device will be given up to an additional 4 hour-period to bring the patient to normothermia ($\leq 37.5^{\circ}\text{C}$). Once the subject's core temperature is $\leq 37.5^{\circ}\text{C}$, the device will be considered in steady state. Only the total steady state time will be used for analysis. Subjects who are disconnected from the CoolStat for transport may be given a bolus of cold saline before transport. This will be determined by the clinical provider a case-by-case basis.

The COOLSTAT does not have a re-warming function. If the subject's core temperature drops below 36°C , warming therapies can be initiated at the discretion of the Investigator or the attending clinician(s). The subject can stay on the COOLSTAT and continue with the study as long as core temperature can be adequately controlled at the discretion of the Investigator or the attending clinician(s). Any change to therapy must be recorded in the case report form. COOLSTAT therapy will be discontinued if tympanic temperature drops below 34°C for a sustained period of at least 5 minutes.

The CoolStat nasal mask will be removed at least every 4 hours to inspect nasal tissue for the development of any pressure sores. Petroleum gel may be applied to facilitate a strong seal below the nasal mask pillows and the nostrils without requiring much pressure from the mask straps.

The COOLSTAT therapy will be discontinued at the end of Phase 1, at which point the subject can be placed on alternate cooling therapies at the discretion of the attending clinician.

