Statistical Methodology	
The primary efficacy analysis for temperature maintenance will be based on the evaluable population of subjects who achieve normothermia by 4 hours and continue cooling treatment with the COOLSTAT System.
 
The proportion of subjects fulfilling success criteria and 90% confidence intervals will be reported and compared to the a priori minimum acceptable criteria:
 
 • at least 75% of the subjects will reach normothermia (core temperature $\leq 37.5^{\circ}\text{C}$) within 4 hours of starting COOLSTAT cooling, and • at least 75% of the subjects' core temperatures remain between 36°C and 37.5°C for 80% of the steady state time following the initial achievement of 37.5°C. 
All adverse events (AEs) reported during the study will be presented in tabular format to include: time of onset, whether or not the patient continued in the study, the nature of intervention and resolution. The potential contribution to the AE by the device will be assessed by the attending physician who reports the AE and the investigator.

Data Safety Monitoring Board	
A DSMB will be formed to monitor this study. The DSMB will meet: 1) before any subjects are enrolled (to review the study), 2) after the first 5 subjects (all with ICP monitoring), 3) after the first 10 subjects (before proceeding to 24-hour

upon being reconnected to the CoolStat is $\leq 37.5^{\circ}\text{C}$. If the subject's temperature is $> 37.5^{\circ}\text{C}$ upon being reconnected to the device, the device will be given up to an additional 4 hour-period to bring the patient to normothermia ($\leq 37.5^{\circ}\text{C}$). Once the subject's core temperature is $\leq 37.5^{\circ}\text{C}$, the device will be considered in steady state.

cooling treatment), 4) after each 6-month period of study, 5) at the end of the study, and 6) after any serious adverse event.

A clinical monitor will also be used to periodically visit the study sites and monitor the activities of the study to ensure that the study protocol, consent activities and data collection are being completed in accordance with specified procedures.

The Clinical Monitor and DSMB will be comprised of:

- [name] - Clinical Monitor
- [name] (Johns Hopkins) - Chair of DSMB - Voting Member
- [name] (Johns Hopkins) - DSMB Voting Member
- [name] (UMMC) - DSMB Voting Member
- [name] (UMMC) - DSMB Voting Member
- [name] (UMMC) - PI (Non-Voting Member)

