6.3 Primary Efficacy Endpoint and Success Criteria

This feasibility study should confirm that the COOLSTAT system has the ability to safely and adequately achieve and maintain normothermic cooling therapy with its control system over a specified period for subjects who were enrolled in the study.

This cooling aspect of the trial will be considered a success if at least 75% of the subjects achieve the following criteria:

- Cooling Performance: The subjects reach normothermia (core temperature $\leq 37.5^{\circ}\text{C}$) within 4 hours of starting COOLSTAT cooling.
- Temperature Maintenance: The subjects are held within a 1.5°C temperature band, between $36^{\circ}\text{C} - 37.5^{\circ}\text{C}$, for 80% of the steady state time following the initial achievement of 37.5°C .³

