13.0 Statistical Analysis Plan

The primary efficacy analysis for cooling performance will be based on the evaluable populations of subjects who undergo cooling treatment with the COOLSTAT System. Analysis will be performed on treatment initiated and treatment completed populations. Subjects who achieve normothermia (core temperature $\leq 37.5^{\circ}\text{C}$) within 4 hours of starting COOLSTAT treatment and maintain normothermia for the duration of the treatment will be determined to have been treated successfully.

The primary efficacy analysis for temperature maintenance will be based on the evaluable population of subjects who maintain normothermia (core temperature between 36°C and 37.5°C) for at least 80% of the time following the initial achievement of 37°C will be determined to have been treated successfully.

The proportion of subjects fulfilling success criteria and 90% confidence intervals will be reported and compared to the a priori minimum acceptable criteria:

- at least 75% of the subjects will reach normothermia (core temperature $\leq 37.5^{\circ}\text{C}$) within 4 hours of starting COOLSTAT cooling, and
- at least 75% of the subjects' core temperatures remain between 36°C and 37.5°C for 80% of the steady state time following the initial achievement of 37.5°C .

Continuous measurements will be summarized using the mean and standard deviation. Categorical variables will be reported using percentages and confidence intervals. Data collected will be plotted to demonstrate the change in core temperature from baseline.

An exploratory analysis of participant subgroups will be performed, stratified by stroke presentation (ischemic versus hemorrhagic). Cooling performance and AEs will be evaluated by subgroup.

Double nostril air flow and single nostril air flow subjects will not be merged or directly compared. The results from subjects treated with single nostril flow will be analyzed separately from subjects treated with double nostril air flow.

Subjects 1 through 20 will be assigned to the double nostril air flow treatment group:

- Subjects 1 through 10 will be treated for 8 hours (N=10)
- Subjects 11 through 20 will be treated for 24 hours (N=10)

Subjects 21 through 30 will be assigned to the single nostril air flow treatment group

- Subjects 21 through 30 will be treated for 24 hours (N=10).
- Subjects 21 through 30 will be treated using a dose escalation model:
 - Dosing for this cohort (flow rate) will begin at 30 LPM.

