13.1 Primary Performance Outcome Analysis

The primary hypothesis regarding cooling performance is that at least 75% of the subjects will reach normothermia (core temperature $\leq 37.5^{\circ}\text{C}$) within 4 hours of starting COOLSTAT cooling.

The primary hypothesis regarding temperature maintenance is that at least 75% of the subjects' core temperatures remain between 36 °C and 37.5 °C for 80% of the steady state time following the initial achievement of 37.5 C.

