14.3 Urgent Change in Therapy

If it is determined by the investigator that alternate cooling methods are required, the subject is removed from COOLSTAT therapy but data will continue to be manually collected according to the schedule outline starting in Phase 2 and continuing through the remainder of the protocol to subject completion.

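### Temperature maintenance: loss of control after normothermia is not counted as a failure when the subject is switched or stopped early

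*Combined protocol and SAP*

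**What the plan says.** **Endpoint.** Section 13.1 states the maintenance hypothesis as 75% of subjects staying within 36 to 37.5 °C "for 80% of the steady state time following the initial achievement of" 37.5 °C. Section 6.3 ties study success to it: "This cooling aspect of the trial will be considered a success if at least 75% of the subjects achieve the following criteria". Section 6.10 requires 8 of the first 10 subjects to meet it before cooling is extended to 24 hours.

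**Time base.** Steady state is described only for subjects disconnected for transport (synopsis footnote and Section 9.3). Once a reconnected subject is at or below 37.5 °C, "the device will be considered in steady state". The paragraph then says "Only the total steady state time will be used for analysis". No end of the window is given. Section 13.0 also has a different version, "for at least 80% of the time following the initial achievement of 37" °C, which does not mention steady state.

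**Population.** The synopsis bases the maintenance analysis on "subjects who achieve normothermia by 4 hours and continue cooling treatment with the COOLSTAT System". Section 13.0 names treatment-initiated and treatment-completed populations, defines neither, and does not say which governs maintenance.

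**Failure rule.** There is only one, in Section 9.3, for a subject who does not reach 37.5 °C within 4 hours: "The subject will be classified as a treatment failure and placed on standard of care treatment".

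**Stops and switches after normothermia.** Section 14.3: "If it is determined by the investigator that alternate cooling methods are required, the subject is removed from COOLSTAT therapy". Sections 5.1.2, 9.3 and 10.3 allow this at any time. Section 5.2 adds temperature stops: core above 39.5 °C or below 36 °C for 5 minutes, and above 39.0 °C for more than 4 hours. None of these sections says how such a subject is scored for maintenance.

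**The concern.** The maintenance endpoint asks whether the device can hold normothermia over the treatment period. The subjects who bear most directly on that question are those who reach 37.5 °C, lose control and need another method. Under the stated rules they leave the denominator, are judged only on the time before the switch, or are credited with cooling that another device delivered. Each of these makes the result more favourable than counting them as failures.

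The switch is made at the discretion of investigators who know the treatment, so the length of the scored window depends in part on their decisions. Section 6.8 argues that bias is not a significant concern because success rests on temperatures and pre-specified criteria. That argument needs a window fixed in advance. At stake are one of two primary hypotheses and one of the criteria for moving to 24-hour cooling.

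**Working it through.** **The plan's own figures.** Section 6.6: ((1.28·√(0.9·0.1) + 0.84·√(0.75·0.25))/0.15)² = 24.85, rounded up to 25. This reproduces and is not in dispute. Section 6.10: 0.75 × 10 = 7.5, rounded up to 8. This also agrees.

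**Inputs.** Threshold 80%, band 36 to 37.5 °C (13.1); planned duration 8 h for subjects 1–10 and 24 h for subjects 11–30 (13.0); temperature stops (5.2).

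**Condition for passing on a window cut at the switch.** t_in/(t_in + t_out) ≥ 0.80 is the same as t_in ≥ 4 × t_out. So 5 min out of band needs 20 min in band, 0.5 h needs 2 h, 1 h needs 4 h, and 4 h needs 16 h.

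**One subject, four readings.** Illustration: normothermic at 2 h, 2.0 h in band, 0.5 h out, then switched.

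| Reading | 24 h subject | 8 h subject |
|---|---|---|
| Not in the population (synopsis) | dropped | dropped |
| Window ends at the switch | 2.0/2.5 = 80%, success | 2.0/2.5 = 80%, success |
| Window runs on, later time in band credited | 21.5/22 = 97.7%, success | 5.5/6 = 91.7%, success |
| Planned window, time after the switch not maintained | 2.0/22 = 9.1%, failure | 2.0/6 = 33%, failure |

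**Which stops can give a success on a shortened window?**

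- *Discretionary switch.* No minimum time out of band is required, so this route is open at both durations.
- *Core below 36 °C for 5 min.* Twenty minutes in band beforehand is enough: 20/25 = 80%.
- *Core above 39.5 °C for 5 min.* Assume a linear rise from 37.5 °C at r °C/h. Then t_out = 2/r + 5/60 h. For r = 0.5, 1, 2 and 4, t_out is 4.1, 2.1, 1.1 and 0.6 h. The in-band time needed is 16.3, 8.3, 4.3 and 2.3 h. At 8 hours of treatment only the two faster rises fit.
- *Core above 39.0 °C for 4 h.* An 8 h subject cannot pass: at most 4/8 = 50%. A 24 h subject needs at least 16 h in band first. With normothermia at 2 h, 16/20 = 80% on the shortened window and 16/22 = 72.7% on the planned one.

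**Study level (illustration).** The documents give no rate of switching. Assume that the device truly holds 70% of subjects, and that a further 10 percentage points lose control and are switched early. Assume also that all 20 double-nostril subjects enter the analysis (13.0 analyses the single-nostril subjects separately).

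- Switched subjects scored as failures: 14/20 = 70%, criterion missed.
- Switched subjects dropped: 14/18 = 77.8%, criterion met.
- Switched subjects scored as successes: 16/20 = 80%, criterion met.

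Binomial chance of meeting the criterion when the stated points are rescored as success:

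| Points rescored | At least 8/10 | At least 15/20 |
|---|---|---|
| 0 | 38% | 42% |
| 5 | 53% | 62% |
| 10 | 68% | 80% |
| 15 | 82% | 93% |

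**The case against.** The strongest objection is that the cut-off window is inferred. The steady-state text in the synopsis footnote and in Section 9.3 concerns transport. A reader might infer that every switch ends the maintenance clock, but no section says so. This stands: a shortened window is one open reading among several.

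Second, Section 13.0 calls a subject successfully treated who reaches normothermia within 4 hours and keeps it throughout treatment. The same section lists durations of 8 and 24 hours. If planned duration is meant, a subject removed for returning fever is not a success. A reader might infer that no reading at all gives failure, and this sentence shows that to be too strong. But it does not say planned duration, it sits in the paragraph on cooling performance, and the next paragraph gives maintenance a different rule.

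Third, a reader might infer that faster rescue always improves the score. It does not under the synopsis population, where the subject is dropped. The 4-hour stop above 39.0 °C cannot produce a false success in an 8 h subject either. Nor is a stop for blood pressure, in a subject whose temperature was in band, a failure to hold temperature.

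Finally, this is a feasibility study. Emergency changes of therapy need an adverse event form, insufficient cooling is a listed event, and the DSMB reviews the case report forms before 24-hour cooling. Rescue would therefore be visible to a careful reader, but it would still not enter the maintenance proportion or the 8-of-10 count.

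**Conclusion.** The concern holds in this form: the maintenance analysis contains no rule that counts loss of temperature control after normothermia as failure. The synopsis population can drop a switched subject. Steady-state time read as time on the device scores that subject on a shortened window. A window that runs on credits CoolStat with another method's cooling. Only one sentence in Section 13.0 might point the other way, and it is not explicit. This is more than missing detail, because each of the first three readings favours the device.

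For one subject the difference can be 80% against 9% (24 h) or 33% (8 h). For the study, the shift from 70% to about 78% or 80% rests on an assumed 70% true rate and 2 switched subjects in 20. The actual frequency is unknown. The main routes are discretionary switches and the 5-minute temperature stops. The documents do not support the stronger statement that switching is defined to end the clock.

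**What to change.** In the synopsis and Sections 6.3, 6.10 and 13.0:

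1. Make the primary maintenance population all treated subjects who reach 37.5 °C within 4 hours. Delete continued CoolStat treatment as a condition of entry.
2. Define the window as running from first 37.5 °C to the planned end of Phase 1 (8 h or 24 h). Exclude transport time and the re-cooling time after reconnection that Section 9.3 already leaves out.
3. Score as a maintenance failure any subject switched to alternative cooling, or stopped for insufficient temperature control, before the planned end.
4. For stops for other adverse events (such as blood pressure or ICP), or because cooling is no longer needed (10.3), use time to the stop and report counts by reason. Add a sensitivity analysis that scores the adverse-event stops as failures.
5. Apply the same scoring to the 8-of-10 criterion.
6. Reconcile the synopsis, 9.3, 13.0 and 13.1, including 37 against 37.5 °C as the start. Sections 5.2 and 9.3 also differ on whether CoolStat stops when core temperature falls below 36 °C; those passages must be reconciled as well.

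No rule on when to stop or switch a subject changes. The data are already planned: core temperature is logged each second (12.6), changes of therapy go on the case report form (9.3), and manual readings continue after removal (14.3). The cost is a protocol amendment, which Section 14.15 sends to FDA before use, and a maintenance proportion that may be less favourable.
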